13 STATISTICAL METHODS AND CONSIDERATIONS

Prior to the analysis of the final study data, a detailed Statistical Analysis Plan (SAP) will be written describing all analyses that will be performed. The SAP will contain any modifications to the analysis plan described below.

13.1 Study design/Endpoints

The primary objective of this open label randomized phase II study is to evaluate the efficacy and tolerability of topical compounded dexamethasone solution in a Mucolox™ for the treatment of Oral Inflammatory Ulcerative Diseases. The primary endpoint will be a change from pre to post treatment in each subject's subjective sensitivity score (0-10) evaluated at baseline and 4 weeks post treatment for each arm. We will also compare changes of the daily subject's subjective sensitivity score (0-10) over time for each arm.

The secondary objectives include the evaluation of objective data using the REU scoring system and the oral health related quality of life using the OHIP-14.

13.1.1 Analysis of Primary Endpoints

VAS scores will be summarized descriptively for each arm at pre-treatment, post-treatment, and pre-to-post treatment change. The pre-to-post treatment change will be compared between the arms using either Student's t-test or Mann-Whitney test, depending on the distribution of the data.

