EFFICACY EVALUATIONS	
PRIMARY ENDPOINT	
 Change from pre to post treatment in each subject's subjective sensitivity score (0-10) evaluated at baseline and 4 weeks post treatment for each arm. We will also compare changes of the daily subject's subjective sensitivity score (0-10) over time for each arm.
SECONDARY ENDPOINTS	
 The secondary endpoints include the evaluation of objective data using the REU scoring system and the oral health related quality of life using the OHIP-14.
OTHER EVALUATIONS	None
SAFETY EVALUATIONS	The safety of participants and the overall study will be monitored continuously throughout the study period. At the 4 week visit, evaluating doctors will review the participants' diaries for self-reported adverse events.
PLANNED INTERIM ANALYSES	When approximately 50% of patients have completed the study, an interim analysis for safety will be conducted by an independent data monitoring committee. Serious adverse events will be monitored by the committee on an ongoing basis throughout the study.
STATISTICS Primary Analysis Plan	Pre-to-post treatment improvement will be assessed using McNemar's test within each arm. The REU scores will be summarized descriptively for each arm at pre-treatment, post-treatment, and pre-to-post treatment change. The pre-to-post treatment change will be compared between the arms using either student's t-test or Mann-Whitney test, depending on the distribution of the data.
Rationale for Number of Subjects	The sample size was calculated to ensure at least 80% power and two-sided alpha of 0.05 in detecting a t difference of 2.0 points oral pain on an 11 point scale (VAS 0-10) between Arm A and B.

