1.1.2 Dexamethasone solution for Oral Inflammatory Ulcerative Diseases

The efficacy of dexamethasone solution has been well described in several clinical trials. Rhodus et al. conducted a prospective controlled clinical trial to test the efficacy of dexamethasone solution in 13 patients with oral erosive-ulcerative lichen planus²⁷. Patients were instructed to rinse with 5 ml of dexamethasone 0.1% solution for 3 min and then to expectorate. Subjective symptomatology (pain and/or discomfort) was recorded on a 100 mm visual analogue scale (VAS) at first visit and at 6 week follow up. Patients experienced significant subjective improvement in symptoms following the dexamethasone treatment (VAS score pre-treatment: 6.7 ± 1.4 ; VAS score post-treatment: 2.3 ± 0.6).

Hambly et al. conducted a single-blinded, cross-over pilot trial in nine patients to compare the efficacy of compounded dexamethasone solution for OLP²⁸. Patients were instructed to rinse with 2 ml of dexamethasone 0.5 mg/2 mL compounded as a solution or one 0.5 mg tablet crushed and mixed with 20 ml water three times per day for 3 weeks. All patients were instructed to rinse and hold the medication in their mouths for at least 2–3 minutes and then expectorate. Participants were evaluated at weeks 0, 3, 4, and 7. Symptoms were recorded with a 100-mm VAS; other assessments included the Treatment Satisfaction Questionnaire for Medication-9, comparisons of clinical photographs, and self-assessment via patient daily diary (Appendix 2) entries to record compliance with each dose. Results showed the compounded dexamethasone solution to be more effective compared to 0.5 mg dexamethasone tablet crushed and mixed with 20 ml water in terms of compliance, patient-perceived faster onset of action, and improved symptom relief.

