5 CRITERIA FOR EVALUATION

5.1 Primary Efficacy Endpoint

The primary endpoint will be a change from pre to post treatment in each subject's subjective sensitivity score (0-10) evaluated at baseline and 4 weeks post treatment for each arm. We will also compare changes of the daily subject's subjective sensitivity score (0-10) over time for each arm.

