6.2 Inclusion Criteria

1. Male or female ≥ 18 years of age at Visit 1.

2. Patients with symptomatic (worst VAS sensitivity score ≥ 7 over the last week) Oral Inflammatory Ulcerative Diseases
3. Written informed consent (and assent when applicable) obtained from subject or subject's legal representative and ability for subject to comply with the requirements of the study.

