9.2.3 Patient Reported Outcomes

Subjective assessments of subjects' oral symptoms will be obtained by using instruments from the NIH consensus documents for oral cGVHD, a condition that is very similar to other Oral Inflammatory Ulcerative Diseases (see Appendix 3 &4). These include report of mouth sensitivity at rest and sensitivity with stimulation (e.g. eating) on an eleven point scale. For the primary endpoint the worst sensitivity in the past week will be used. The clinician seeing the subject will

complete these forms at each study visit. Patients will also report daily sensitivity on an eleven point scale (see Appendix 2). Tolerability and compliance will also be evaluated, and a patient reported global assessment of overall improvement will be evaluated at the four-week visit.

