13.1.2 Analysis of Secondary Endpoints

Oral health related quality of life will be assessed before and after topical therapy using the 14-item Oral Health Impacts Profile (OHIP-14; see Appendix 5) instrument that measures subject's perceptions of the impact of oral conditions on their well-being. The OHIP-14 scores will be summarized descriptively for each arm at pre-treatment, post-treatment, and pre-to-post treatment change. The pre-to-post treatment change for each item and for all items combined will be assessed within each arm using either paired t test or Wilcoxon-signed-rank test depending on its distribution. In addition, each question will be dichotomized and classified as 'response' if the answer is 'not at all', or 'slightly' to a question such as "how isolated do you feel as a result of this oral condition", and pre-to-post treatment improvement will be assessed using McNemar's test within each arm.

In order to evaluate the clinical improvement in clinician-reported outcome measures for Oral Inflammatory Ulcerative Diseases, REU scores within the compound dexamethasone solution in Mucolox™ group (Arm A) will be compared to that in the dexamethasone solution only group (Arm B). The REU scores will be summarized descriptively for each arm at pre-treatment, post-treatment, and pre-to-post treatment change. The pre-to-post treatment change will be compared between the arms using either student's t-test or Mann-Whitney test, depending on the distribution of the data.

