Appendix 1**INSTRUCTIONS FOR PREPARING & USING YOUR
TOPICAL SOLUTION****WHAT YOU WILL RECEIVE**

- One 480 mL bottle of concentrated solution (5 mg/5 mL)
- 4 tablets of fluconazole 200 mg

USING YOUR SOLUTION

You will be rinsing with your solution **3 times per day**.

1. Gently shake the bottle of solution.
2. Pour 5 mL of solution into the dosing cups provided.
3. Swish the solution in your mouth for 5 minutes, then spit – DO NOT SWALLOW!
4. Do not eat or drink for 15 minutes after rinsing.

Please take one table of fluconazole once a week

CONFIDENTIAL

This document is confidential. Do not disclose or use except as authorized.

	11													
	12													
	13													
	14													

	3													
	15													
	16													
	17													
	18													
	19													
	20													
	21													
	22													
	4													

CONFIDENTIAL

This document is confidential. Do not disclose or use except as authorized.

	23																						
	24																						
	25																						
	26																						
	27																						
	28																						

CONFIDENTIAL

This document is confidential. Do not disclose or use except as authorized.

Appendix 3

DEXAMETHASONE RINSE IN MUCOLOX™ FOR THE TREATMENT OF ORAL INFLAMMATORY ULCERATIVE DISEASES

VISIT #1

Subject Name _____

[figure not shown]
[figure not shown]
Medical Record Number _____

Date of Visit _____

SUBJECTIVE DATA (Over last two weeks unless specified)

MUCOSAL PATHOLOGY

- 1. Does your mouth hurt now? Y/N
- 2. Does it hurt to swallow food or drink? Y/N
- 3. How would you rate your worst mouth sensitivity over the last week?

No sensitivity

Worst sensitivity

CONFIDENTIAL

This document is confidential. Do not disclose or use except as authorized.

[figure not shown]
[figure not shown]
4. Do you avoid any foods because they make your mouth hurt?

- 0 = Not at all
- 1 = Slightly
- 2 = Moderately
- 3 = Quite a bit
- 4 = Extremely

If “yes”, what types of foods?

- a. Spicy foods
- b. Acidic foods
- c. Salty foods
- d. Hard/crunchy/crusty foods
- e. Other:

5. Do you feel that your oral intake (what you eat) is limited by your oral condition? Y/N

Not limited at all

Severely limited

Score: _____

If “Yes”, how limited do you feel it is?

- a. Partial limitation
- b. Severe limitation

6. Have you been bothered by ulcers in the mouth?

- 0 = Not at all
- 1 = Slightly
- 2 = Moderately
- 3 = Quite a bit
- 4 = Extremely

CONFIDENTIAL

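### The synopsis lists secondary analyses as the primary analysis plan, and section 13.1.1 leaves the choice of VAS test open and ignores baseline VAS; one pre-specified ANCOVA, stated in both places, would settle this cheaply.

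*Combined protocol and SAP*

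**What the plan says.** Section 13.1.1 covers the primary VAS endpoint: "The pre-to-post treatment change will be compared between the arms using either Student's t-test or Mann-Whitney test, depending on the distribution of the data". It names no criterion, default test or covariate.

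The synopsis, in its Statistics row under Primary Analysis Plan, says something else: "Pre-to-post treatment improvement will be assessed using McNemar's test within each arm". It then describes REU scores and compares REU change between arms. VAS is not mentioned. In section 13.1.2 McNemar's test is for dichotomised OHIP-14 items, and REU change is compared "using either student's t-test or Mann-Whitney test, depending on the distribution of the data". Both are secondary endpoints.

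The primary variable is fixed in section 9.2.3: "For the primary endpoint the worst sensitivity in the past week will be used". The Visit #1 form in Appendix 3 asks for it at baseline: "How would you rate your worst mouth sensitivity over the last week". Section 6.2 restricts entry to "worst VAS sensitivity score ≥ 7 over the last week".

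The synopsis and sections 5.1 and 13.1 add a second comparison under the primary endpoint, with no method: "We will also compare changes of the daily subject's subjective sensitivity score (0-10) over time for each arm".

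**The concern.** Someone working from the synopsis and someone working from section 13.1.1 would produce different primary analyses. The synopsis version does not answer the primary objective, which is a between-arm difference in symptoms, and it does not match the sample size, which rests on a between-arm VAS difference of 2.0 points. McNemar's test also needs paired binary data, and no VAS cut-off is defined.

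Within section 13.1.1 the test behind the primary p-value depends on how the distribution is judged. The t-test concerns a difference in means and Mann-Whitney a shift in ranks, so the reported effect could change with the choice. In an open-label trial that choice can be made with the results in view.

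Comparing raw change fixes the slope of week-4 VAS on baseline VAS at 1. If the true slope is lower, some precision is lost that a covariate would recover at no data cost.

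**Working it through.** **1. The plan's own figure.** Section 13.2 gives a difference of 2.0, an SD of change of 1.4 in each arm, two-sided alpha 0.05, at least 80% power, 15 per arm and 5% loss.

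- Normal approximation: 2 × (1.960 + 0.842)² × 1.4² / 2.0² = 7.7, so 8 per arm. Exact t: 9 per arm (81.2% power); 9/0.95 = 9.5, so 10 enrolled.
- Fifteen per arm is more than these inputs require, and the claim of at least 80% is true. Power is 96.5% at 15 per arm and 95.3% at 14 (15 × 0.95 = 14.25).

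**2. What the documents say about the slope.** They give neither the slope nor the baseline SD for this trial. The only pre/post spread for VAS is in section 1.1.2: "VAS score pre-treatment: 6.7 ± 1.4 ; VAS score post-treatment: 2.3 ± 0.6". With slope b = r × SDpost/SDpre, b ≤ 0.6/1.4 = 0.43 in that study, reached only if r = 1. It had 13 patients with one diagnosis, seen at 6 weeks on a different solution strength. Treating the two SDs as independent, an F(12,12) range for the ratio is 0.24-0.78.

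**3. Baseline SD (assumed).** Entry at 7 or more confines scores to 7-10. An even split between 7 and 8 gives SD 0.5, equal use of 7, 8, 9 and 10 gives 1.12, and an even split between 7 and 10 gives the ceiling of 1.5. The range used is 0.5-1.5.

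**4. ANCOVA against change score, 14 per arm.**

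- Change score: half-width of the 95% CI = t(26) × SD × √(2/14), which is 1.088 for SD 1.4 and 1.554 for SD 2.0 (an assumed, less favourable value).
- ANCOVA: residual variance = SD² − (1 − b)² × SDb². The variance is multiplied by 1 + 1/24 for estimating the slope, and the half-width uses t(25).
- Example (SD 1.4, SDb 1.12, b = 0.43): 1.96 − 0.57² × 1.12² = 1.552; 1.552 × 25/24 = 1.617; 1.617/1.96 = 0.825, so variance is 17.5% lower.

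At b = 0.43:

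| Baseline SD | Half-width, SD 1.4 | Variance | Half-width, SD 2.0 | Variance |
|---|---|---|---|---|
| 0.5 | 1.089 | −0.2% | 1.573 | +2.1% |
| 0.7 | 1.066 | −4.3% | 1.557 | 0.0% |
| 0.9 | 1.035 | −9.8% | 1.536 | −2.7% |
| 1.12 | 0.990 | −17.5% | 1.506 | −6.4% |
| 1.5 | 0.881 | −34.7% | 1.436 | −14.9% |

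- Break-even slope = 1 − 0.2 × SD/SDb. For SD 1.4 and baseline SD 0.7, 0.9 and 1.12 it is 0.60, 0.69 and 0.75. Above break-even ANCOVA is slightly worse, by at most 1/24 = 4.2% in variance at slope 1.
- Power at a true difference of 1.5, b = 0.43, baseline SD 0.7-1.12: from 77.9% to 79.5-85.1% for SD 1.4, and from 48.0% to 47.9-50.5% for SD 2.0.

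**5. The missing selection rule, by simulation.** Assumptions: 14 per arm, integer baselines 7-10, slope 0.43, SD of change 1.4 or 2.0, scores rounded and clipped to 0-10. Two Shapiro-Wilk rules were compared, one applied to each arm and one to pooled residuals. Neither is in the documents.

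- The rules chose different tests in 19-33% of trials but gave different significance verdicts in only about 0.3-2%.
- The t-test and Mann-Whitney disagreed at 0.05 in 4.3-6.5% of trials when the true difference was 1.0-1.5, and in 1.6-1.9% under no difference.
- Type I error was 5.2-5.6% for the data-chosen test and 5.2-5.4% for the t-test, with Monte Carlo error of about 0.7 points.

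**The case against.** The strongest reply is that the endpoint is defined as change and the sample size uses the SD of change, so a test of change is coherent and ANCOVA is a preference. Part of this stands: the change-score test is not wrong, power is ample, and the documents cannot settle whether ANCOVA gains or loses a little. The 0.43 slope is an upper bound from a small study; at 0.78 with SD 1.4, ANCOVA has 1-3% more variance for baseline SD 1.12-0.7. The endpoint does not stand in the way, however. With baseline in the model, the arm coefficient is the same whether week-4 VAS or change is the outcome.

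A second reply is that section 13 promises a detailed SAP before the final analysis. That SAP could supply a selection rule and a method for the daily scores. It is required only before analysis of the final data, in an open-label trial, and the promise does not remove the conflict between the synopsis and section 13.1.1.

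Third, the synopsis closely repeats sentences from section 13.1.2, so it looks like a copying slip. That is likely, and it makes the correction easy, but the text still needs correcting.

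Some stronger readings are tempting and are not supported:

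- **Inflated type I error.** The simulations show no material inflation under either rule.
- **An unstable conclusion.** The 19-33% counts tests chosen, not verdicts changed.
- **A large precision gain.** Large reductions need a slope near 0 or a baseline SD near its ceiling, and the documents establish neither.
- **No between-arm VAS test anywhere.** Section 13.1.1 does contain one.

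**Conclusion.** The synopsis entry is wrong as written and conflicts with section 13.1.1, the primary objective and the sample size basis. That part rests on the text alone.

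The missing selection rule is a pre-specification gap that seldom changes the conclusion. Leaving out baseline VAS costs a probably modest amount of precision. At 14 per arm and slope 0.43, over baseline SD 0.5-1.5, the variance change from ANCOVA is about 0-35% lower for SD of change 1.4, and from 2% higher to 15% lower for SD 2.0. Slope, baseline SD and the 2.0 are assumptions. The downside is one degree of freedom and at most about 4% more variance. With planned power at 95-96%, the benefit is mainly a narrower interval.

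A reader might infer that ANCOVA would make the comparison unbiased. It would not: it does nothing about the exclusion and replacement of patients after randomisation (sections 9.2, 12 and 12.4). The change should be made as a low-cost improvement together with a correction of the synopsis.

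**What to change.** Before outcome data are examined, put the same text in the synopsis, section 13.1.1 and the SAP:

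- **Primary analysis:** ANCOVA of week-4 worst-sensitivity VAS on arm with baseline VAS as covariate, reporting the adjusted mean difference with its 95% CI.
- **Sensitivity analysis:** Mann-Whitney on change, reported whatever the distribution.
- **Synopsis:** replace the Primary Analysis Plan with the above, and list McNemar's test and REU as secondary, as in section 13.1.2.
- **Daily scores:** label the comparison supportive in the synopsis and sections 5.1 and 13.1, and name its method.

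Baseline REU as a covariate for REU is optional; the documents give no REU SD, so its gain cannot be sized. If the team prefers the change-score t-test, naming it as the single primary test closes the missing rule without the possible precision gain.

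The cost is wording in those sections and in the SAP already promised. No new data, visits or patients are needed.

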13.1.2 Analysis of Secondary Endpoints

Oral health related quality of life will be assessed before and after topical therapy using the 14-item Oral Health Impacts Profile (OHIP-14; see Appendix 5) instrument that measures subject's perceptions of the impact of oral conditions on their well-being. The OHIP-14 scores will be summarized descriptively for each arm at pre-treatment, post-treatment, and pre-to-post treatment change. The pre-to-post treatment change for each item and for all items combined will be assessed within each arm using either paired t test or Wilcoxon-signed-rank test depending on its distribution. In addition, each question will be dichotomized and classified as 'response' if the answer is 'not at all', or 'slightly' to a question such as "how isolated do you feel as a result of this oral condition", and pre-to-post treatment improvement will be assessed using McNemar's test within each arm.

In order to evaluate the clinical improvement in clinician-reported outcome measures for Oral Inflammatory Ulcerative Diseases, REU scores within the compound dexamethasone solution in Mucolox™ group (Arm A) will be compared to that in the dexamethasone solution only group (Arm B). The REU scores will be summarized descriptively for each arm at pre-treatment, post-treatment, and pre-to-post treatment change. The pre-to-post treatment change will be compared between the arms using either student's t-test or Mann-Whitney test, depending on the distribution of the data.

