8 STUDY TREATMENTS

8.1 Method of Assigning Subjects to Treatment Groups

Randomization will be predetermined by a computer-generated list and coordinated by the UCSF Investigational Drugs Services Pharmacy. Patients will be assigned to one of two groups: 1) Arm A: compounded dexamethasone 0.5mg/5ml solution in Mucolox™ or 2) commercial dexamethasone 0.5mg/5ml solution only (ARM B).

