13.2 Sample Size, Accrual Rate and Study Duration

The sample size was calculated based on the data by Rhodus et al., as to ensure at least 80% power and two-sided alpha of 0.05 in detecting a t difference of 2.0 points oral pain on an 11 point scale (VAS 0-10) between Arm A and B²⁷. The mean expected change for Arm A will be 6.5 points reduction with a standard deviation of 1.4 points. The mean expected change for Arm B will be 4.5 points reduction with a standard deviation of 1.4 points.

A total of 15 patients per arm will be enrolled (total of 30 subjects). The proposed sample size includes a loss of follow up of 5%. Approximately 60 patients per year are diagnosed with Oral Inflammatory Ulcerative Diseases at the Sol Silverman Oral Medicine Clinic at UCSF. We anticipate the accrual rate will be approximately 2 patients per month, thus the accrual goal will be achieved in approximately 15 months.

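### OHIP-14 is analysed only by 58 unadjusted within-arm tests, with no lead measure and no comparison between arms, so lists of p-values may be read as a treatment difference

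*Combined protocol and SAP*

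**What the plan says.** Section 13.1.2 measures quality of life with the "14-item Oral Health Impacts Profile (OHIP-14; see Appendix 5) instrument". It orders two sets of tests:

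- **Paired tests.** "The pre-to-post treatment change for each item and for all items combined will be assessed within each arm", by paired t or Wilcoxon signed-rank test depending on the distribution.
- **McNemar tests.** "In addition, each question will be dichotomized and classified as" a response if the answer is 'not at all' or 'slightly', with a question about feeling isolated as the example. Then "pre-to-post treatment improvement will be assessed using McNemar's test within each arm".

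No section gives a multiplicity adjustment, an order of testing, a lead OHIP-14 measure, or a label of exploratory or descriptive. No OHIP-14 result is compared between arms. By contrast, Section 13.1.1 compares the VAS change between arms, and Section 13.1.2 does the same for REU. The opening of Section 13 promises a detailed SAP before the final analysis; no separate SAP text is in the documents.

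**The concern.** The trial is randomised, but the only OHIP-14 inference is two parallel lists of within-arm p-values. A within-arm test mixes the drug effect, the vehicle effect and regression to the mean, and it cannot say whether Mucolox adds anything. With 29 p-values per arm and 15 patients per arm, some items will be significant in one arm and not in the other even if both arms respond alike. That pattern invites a claim of superiority that no planned test supports.

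The total score, which is the instrument's summary, has no priority over any single item. The McNemar set tests the same item data a second time after reducing five levels to two, at a cut that is not defined on the OHIP-14 response scale.

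**Working it through.** The plan states no test count or error rate for OHIP-14, so there is no figure of its own to reproduce.

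**Inputs**
- 14 items, each scored 0–4 (Section 13.1.2, Appendix 5); total score range 0 to 14 × 4 = 56.
- Two arms: "Patients will be assigned to one of two groups" (Section 8.1). Fifteen patients per arm (Section 13.2).
- Alpha: Section 13.2 gives "at least 80% power and two-sided alpha of 0.05", but only for the "difference of 2.0 points oral pain on an 11 point scale (VAS 0-10) between Arm A and B". Using 0.05 for each OHIP-14 test is an assumption.
- Inter-item correlation: not in the documents; assumed 0 to 0.7.

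**1. Count.** Per arm: 14 items + 1 total = 15 paired tests, plus 14 McNemar tests = 29. Two arms: 58, of which 56 are item-level and 2 are on the total.

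**2. Simple reference under no change.** 58 × 0.05 = 2.9 false positives expected. With independent tests, P(at least one) = 1 − 0.95^58 = 94.9%. The tests are not independent, because items correlate and each is tested twice, so this is not the plan's actual rate.

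**3. McNemar version.** The plan does not say which version it means.
- Exact, all k switches one way: p = 2 × 0.5^k. Five of five gives 0.063; six of six gives 0.031. Its true size never exceeds 0.039 with up to 15 discordant pairs.
- Uncorrected asymptotic: (b − c)²/(b + c). Four of four gives 16/4 = 4.0, p = 0.046.

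**4. Simulation under no change.** Both arms, 15 patients each, 4,000 replicates. Assumptions: a common inter-item correlation; half of each item's latent variance stable between visits; category shares of 20, 20, 25, 22 and 13%; paired t-tests for the 15 change scores per arm; a score of 0 or 1 counted as response.

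| Inter-item correlation | Exact McNemar: expected false positives | P(≥1) | Asymptotic McNemar: expected false positives | P(≥1) |
|---|---|---|---|---|
| 0 | 1.70 | 79% | 2.88 | 90% |
| 0.3 | 1.74 | 74% | 2.92 | 89% |
| 0.5 | 1.70 | 66% | 2.82 | 83% |
| 0.7 | 1.79 | 56% | 2.95 | 75% |

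**5. Identical response in both arms.** Let π be the chance that a given item test is significant, the same in each arm. The chance that it is significant in exactly one arm is 2π(1 − π). The π values below are illustrations, because the documents give no item-level data. Expected discordant items among 14, for one set of tests:
- π = 0.05 (no change): 2 × 0.05 × 0.95 = 0.095; 14 × 0.095 = 1.3.
- π = 0.5 (the maximum): 0.50; 14 × 0.50 = 7.0.
- π = 0.8: 2 × 0.8 × 0.2 = 0.32; 14 × 0.32 = 4.5.

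Real improvement of moderate size therefore produces more misleading contrasts than no change does.

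**6. The McNemar cut.** Section 13.1.2 uses 'not at all' and 'slightly' and an isolation question. Appendix 5 runs from Never (0) to Very Often (4) and has no isolation item. The labels in Section 13.1.2 do appear on the visit forms (Appendices 3 and 4, questions 4 and 6), but those questions are not part of OHIP-14.

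**7. After a change.** One between-arm test: error rate 5%. Testing the total once in each arm instead: 1 − 0.95² = 9.75%, with the arm comparison still missing.

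**The case against.** The strongest reply is that no change is not the expected state. Both arms receive an active steroid, patients enter with a worst sensitivity of at least 7, Section 13.2 expects falls of 6.5 and 4.5 points in sensitivity, and Section 1.1.3 reports symptom improvement in both arms of the preliminary study. A reader might infer from 58 tests that about three results will be false, or that significant items will mostly be chance findings. The documents do not support that. Many significant items would reflect real change or regression to the mean, and the false-positive figures are only a reference case. This objection stands, and it moves the weight of the point to the missing arm comparison.

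Other stronger readings also fail:
- **That McNemar needs six one-way switches and so can rarely be significant.** Six is the threshold for the exact test only, and the documents give no item response rates from which to judge 'rarely'.
- **That the plan forces a t-test on ordinal items.** The same sentence offers the Wilcoxon signed-rank test.
- **That there is no summary result.** The total is tested in each arm; what it lacks is priority and a comparison between arms.

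It is also fair to say that the OHIP-14 objective in Section 3.2 is not worded as a comparison, that this is a secondary endpoint in a 30-patient phase II trial, and that the promised SAP could set a hierarchy. These points limit the weight of the concern. They do not remove it, because the current text orders the tests and leaves their reading open.

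**Conclusion.** The point holds as one of interpretation for a secondary endpoint. The count of 58 is exact. Under no change and 0.05 per test, about 1.7 to 2.9 false positives would be expected and the chance of at least one is 56–90%; the range depends on the McNemar version and on the assumed correlation and item distribution. The 94.9% figure needs independence and should not be quoted as the actual rate.

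The larger problem does not depend on the no-change assumption: within-arm p-values cannot show an arm difference, and the layout invites that reading. Separately, the response rule behind 28 of the 58 tests is not defined on the Appendix 5 scale. A reader should not infer that the trial's main conclusion is at risk; the primary comparison in Section 13.1.1 is untouched.

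**What to change.** In Section 13.1.2, or in the SAP before any data are analysed:

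1. Make change in the OHIP-14 total (0–56) the only tested quantity for this endpoint, compared between arms with one test fixed in advance. The comparison must be between arms, as for VAS and REU; a within-arm test of the total would leave the 'significant in A, not in B' reading in place.
2. Report the within-arm change in the total and the 14 items descriptively, with confidence intervals and no p-values. Label them descriptive, since intervals can also be read as tests.
3. Delete the item-level paired tests and the McNemar tests, and align the synopsis, which lists a within-arm McNemar test under the primary analysis plan without naming an endpoint.
4. Word the OHIP-14 objective in Section 3.2 as a comparison.

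Adjusting all 58 tests instead would serve little purpose. Bonferroni needs p < 0.05/58 = 0.00086, which exact McNemar reaches only with 12 of 12 switches one way (2 × 0.5^12 = 0.00049; 11 of 11 gives 0.00098).

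The cost is a few lines of text and no new data. The team loses item-level p-values to quote. The single test will also be modest in power: 15 per arm gives 80% power for a difference of 2.0 when the SD is 1.887, that is 2.0/1.887 = 1.06 SD. The documents give no OHIP-14 SD to turn this into points.
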